7.6 Interim Analysis

No interim analyses are planned for this study.

7.7 Sample Size Justification

15 patients will be enrolled in each treatment group.

Sample size rationale:

The sample size calculation was based on an expected change from baseline at 4 weeks in TBUT score of 1.5 seconds with a standard deviation of 1.9 seconds within each study group.

Sample size justification:

A sample size of 15 will have 80% power to detect a difference in means of 1.5 assuming a standard deviation of differences of 1.9 (effect size of 0.78), using a paired t-test with a 0.05 two-sided significance level.

Reference:

7.8 **Poolability Analysis**

Patient demographic characteristics and background variables shall be summarized. To ensure poolability in case of more than one site, primary effectiveness will be analysed by site.

7.9 Safety Analyses

The incidence rate of device-related adverse events will be calculated along with 95% CI. The reporting period is from baseline through the last study visit.

Secondary safety endpoint:

- The evaluation of discomfort and pain will be summarized in appropriate tables by visit.
- Changes from baseline in ocular surface staining, and intraocular pressure will be calculated along with 95% CI by study group and visit. The Paired T-test or Signed rank test for two means (paired observations) (as is appropriate) will be applied for testing the statistical significance of the changes within the study group.
- Cornea OCT evaluation to detect changes (cornea thickness, cornea deamination) following treatment. Changes in Cornea OCT evaluation will be summarized in descriptive tables for the Tixel group.

Adverse events will be coded using the Medical Dictionary for Regulatory Activities (MedDRA, most updated version) terminology and presented in tables by System Organ Class (SOC) and Preferred Term (PT).

AE data will be listed individually and summarized by SOC and by PT within a system organ class.

Treatment-emergent adverse events (TEAEs) are those with onset after initiation of study intervention or if occurring prior to initiation of study intervention, worsened after initiation of study intervention. Only treatment-emergent events will be summarized. All events in the clinical database regardless of when they occurred will be provided in a data listing. Definitions of adverse events, serious adverse events, and categorizations of events can be found in Appendix D.

An overall summary will be presented which gives the number and percentage of patients that experienced any TEAE (overall, ocular, and non-ocular), experienced any treatment related TEAE (overall, ocular, and non-ocular), permanently discontinued treatment due to a TEAE (overall, ocular, and non-ocular), interrupted treatment due to a TEAE (overall, ocular, and non-ocular), experienced a treatment emergent serious TEAEs (overall, ocular, and non-ocular), and that died.

A listing of serious TEAEs will be provided. Continuous safety endpoints shall be summarized using summary statistics such as means, medians, standard deviations, minima, maxima, and relevant percentiles.

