4.2 Description of the Study

This study is a randomized, open-label, pilot clinical study comparing the Tixel device to an active control, which will be the LipiFlow System. The goal of this study is to compare between the Tixel device and the LipiFlow System and estimate the magnitude of the differences, if they exist, in terms of safety and effectiveness. A total of up to 30 patients (60 eyes) will be randomized for bilateral treatment and will be assigned in a 1:1 ratio into the Tixel treatment group or the control group at up to 2 study sites in Israel and/or Europe. The evaluator will be masked as to the randomization assignments. Both eyes will receive the same randomized assignment and both eyes of each patient will be evaluated at all time points. One eye will be selected as the designated "study eye" for statistical purposes: The study eye is the eye with the lower baseline TBUT. If both eyes have the same TBUT, the right eye will be the study eye. Outcome Measures

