4.2.3 Primary Safety Endpoint

The primary safety endpoint will be a comparison of the incidence of device-related adverse events (e.g., increase in the lid margin such as development of floppy eyelids, entropion or ectropion; and lash integrity) for the two-treatment arms.

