6.4 Schedule for Study Visits

For the Tixel:

After the randomization to the Tixel arm, each patient will undergo 3 treatment sessions (Day 0, Week 2, Week 4) at 2 weeks intervals (+/-3 days) from the previous treatment, and follow-up sessions at 4-weeks (+/-7 days) and 12-weeks (+/-14 days) after the last treatment session.

For the LipiFlow:

After the randomization to the LipiFlow arm each patient will undergo 1 treatment session (Day 0), and follow-up sessions at 4-weeks (+/-7 days) and 12-weeks (+/- 14 days) after the treatment session.

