7 STATISTICAL CONSIDERATIONS

7.1 General Considerations

Descriptive statistics will be used to summarize continuous variables (number of eyes/patients [N], mean, standard deviation (SD) or standard error of the mean, median, maximum, and minimum) and categorical variables (frequency and percentage) at each assessment timepoint. Statistical comparisons within each group will be performed using appropriate statistical methods or models, and the results such as 95% confidence intervals and p values will be reported. All summary tables will be supported with individual patient and eye data listings. Baseline is defined as the last non-missing observation prior to initiation of study intervention. Analyses will be carried out using SAS software or equivalent statistical software.

Further details will be described in the statistical analysis plan, which will be finalized prior to the study database lock.

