7.2 Analysis Populations

- Intent-to-Treat Population: The intent-to-treat (ITT) population includes all randomized patients. The primary and secondary efficacy analyses will be performed on the ITT population. Patients will be analysed as randomized.
- Per Protocol Population: The per protocol (PP) population includes all patients who have at least one follow-up visit, complete all the treatments as randomized, and have no major protocol deviations. Patients will be analysed as treated.

• Safety Population: The safety population will include all treated patients. The safety population will be analysed for all safety assessments. Patients will be analysed as treated. A summary table of number (%) of patients in each analysis population/set will be provided.

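### The primary safety endpoint compares device-related adverse event incidence between arms, but section 7.9 specifies no between-arm estimate

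*Combined protocol and SAP*

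**What the plan says.** Section 4.2.3 defines the endpoint as a contrast between the two arms: "The primary safety endpoint will be a comparison of the incidence of device-related adverse events". Section 4.2 gives the purpose of the study as comparing the two devices in order to "estimate the magnitude of the differences, if they exist, in terms of safety and effectiveness".

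Section 7.9 gives this endpoint one analysis sentence, "The incidence rate of device-related adverse events will be calculated along with 95% CI", and one on timing, "The reporting period is from baseline through the last study visit". It names no arm, no contrast and no interval method, and it does not say whether the rate counts patients or events. For staining and pressure the same section is explicit about arms: "intraocular pressure will be calculated along with 95% CI by study group and visit".

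Two general provisions bear on this. Section 7.1 states that "Statistical comparisons within each group will be performed using appropriate statistical methods or models" and leaves further detail to a statistical analysis plan to be finalised before database lock. Section 7.2 states that "The safety population will be analysed for all safety assessments", with patients grouped by the treatment they received.

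Section 6.4 sets different regimens. In the Tixel arm, "each patient will undergo 3 treatment sessions (Day 0, Week 2, Week 4) at 2 weeks intervals", with the last visit 12 weeks after the third session. LipiFlow patients have one session and a last visit 12 weeks after it.

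**The concern.** An endpoint defined as a comparison needs an analysis that produces one. Here the endpoint section and the analysis section do not meet: the first calls for a contrast, the second for a rate. Someone programming section 7.9 literally would produce incidence figures and stop. The study report would then lack the quantity that sections 4.2 and 4.2.3 promise, namely an estimated difference in device-related AE incidence with its uncertainty.

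The uncertainty matters most when few events occur. If neither arm has an event, two rates of zero look like equivalence, while the data remain compatible with a sizeable difference in either direction. Only an interval for the difference shows this.

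The schedule raises a related issue. Reporting from baseline to the last visit gives the arms different lengths of observation, so any contrast needs that stated beside it.

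**Working it through.** **Does any section supply the contrast?**
- 4.2.3: the endpoint is a between-arm comparison.
- 4.2: the goal is the size of the difference.
- 7.1: the comparisons described are within arms.
- 7.4: there is a between-arm analysis, but only for change in tear break-up time (TBUT) at 4 weeks.
- 7.9: a rate with an interval for device-related AEs; changes by arm for staining and pressure; descriptive tables for the Tixel arm for corneal OCT; AE summary tables with no arm or contrast mentioned.

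No section specifies a between-arm estimate for device-related AEs.

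**The plan's own design figure.** Section 7.7 gives 80% power for a within-arm paired t-test with n = 15, difference 1.5 s, SD 1.9 s and two-sided 0.05. The noncentrality is (1.5/1.9) × √15 = 3.06 on 14 degrees of freedom, which gives power 0.811. The figure reproduces. It concerns TBUT only; no calculation is given for safety.

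**What the missing estimate would look like.** The inputs are 15 patients per arm (section 7.7) and 95% intervals. The documents give no AE rate, so every count below is an assumption.

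Wilson limits for a proportion p = x/n, with z = 1.96:

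[p + z²/(2n) ± z√(p(1−p)/n + z²/(4n²))] / (1 + z²/n)

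- 0/15: lower limit 0, upper limit 3.841/18.841 = 0.204.
- 3/15: centre 0.328/1.256 = 0.261, half-width 0.191, so 0.070 to 0.452.

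Newcombe limits for d = p₁ − p₂, where l and u are the Wilson limits of each arm:

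- lower = d − √[(p₁ − l₁)² + (u₂ − p₂)²]
- upper = d + √[(u₁ − p₁)² + (p₂ − l₂)²]

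For 3 v 0:
- lower = 0.200 − √(0.130² + 0.204²) = 0.200 − 0.242 = −0.042
- upper = 0.200 + √(0.252² + 0²) = 0.452

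| Patients affected, Tixel v LipiFlow (of 15 each) | Difference, points | Newcombe 95% CI |
|---|---|---|
| 0 v 0 | 0 | −20 to +20 |
| 1 v 0 | +7 | −14 to +30 |
| 3 v 0 | +20 | −4 to +45 |
| 3 v 1 | +13 | −13 to +39 |
| 3 v 3 | 0 | −28 to +28 |

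The widths run from about 41 points (0 v 0) to about 57 (3 v 3). With no LipiFlow events, 4 Tixel patients give a two-sided Fisher p of 0.10 and 5 give 0.042, so a test would add little at this size.

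**Why the method should be named.** For 0 v 0, Agresti-Caffo adds one event and one non-event to each arm. Each proportion becomes 1/17 and the half-width is 1.96 × √[2 × (1/17)(16/17)/17] = 0.158. That is ±16 points against ±20 by Newcombe from the same data.

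**Observation time (section 6.4).** Tixel: third session at week 4, plus 12 weeks, is about 16 weeks with three sessions. LipiFlow: day 0 plus 12 weeks is about 12 weeks with one session. Tixel patients are therefore observed about 16/12 = 1.33 times as long. Visit windows, and any gap between baseline and first treatment, make both figures approximate.

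**The case against.** The strongest reply is that section 7.9 is shorthand. The endpoint refers to two arms, and analysing the safety population by treatment received has little meaning unless results are split by treatment. A reader might infer from the missing arm qualifier that the plan pools the arms into a single rate. The documents do not support that: read together, these provisions point to one rate per arm with a phrase left out. This part of the reply stands. It does not close the gap, because two separate rates with separate intervals still give no interval for the difference.

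A second reply is that section 7.1 defers detail to a statistical analysis plan before database lock. A reader might conclude that the interval method would be picked once the results are known. Nothing in the documents establishes that; the supportable statement is that the supplied text does not yet specify one. The study is open-label, so there is good reason to settle the method well before lock, but that is not evidence of a late choice.

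A third reply is that this is a pilot sized for within-arm TBUT change, with no safety hypothesis or margin. Per-arm rates allow a descriptive comparison, and the point difference follows by subtraction. This limits the severity and rules out asking for a test. It does not remove the point, since estimating the size of differences is what section 4.2 says the study is for.

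**Conclusion.** The point holds as a mismatch between the primary safety endpoint and its planned analysis. The supplied text specifies no between-arm estimate of device-related AE incidence, so following it does not yield the comparison in section 4.2.3. This conclusion rests on the text and not on any event rate. Severity is minor to moderate: the effectiveness analyses are untouched, the data needed are already to be collected, and the resulting estimate will be wide.

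The interval figures rest on 15 treated patients per arm and on assumed counts. They show the precision to expect. They do not suggest a safety signal, and they should not be read as showing that the planned sample is too small for a purpose it was not sized for.

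Any difference reported over the existing window compares regimens as delivered. It mixes device, number of sessions and about four extra weeks of observation in the Tixel arm.

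**What to change.** In section 7.9, or in the statistical analysis plan before database lock:

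1. Report by arm, on the safety population as treated, the number and proportion of patients with at least one device-related AE, each with a 95% CI.
2. Make the primary safety analysis the Tixel minus LipiFlow difference in these proportions, with a 95% CI by one method named in advance (for example Newcombe, with Wilson limits per arm). Label it descriptive, with no test.
3. State beside it that it compares regimens as delivered: three sessions and about 16 weeks of AE observation for Tixel, one session and about 12 weeks for LipiFlow.
4. Add a supportive table restricted to a common 12-week window from first treatment.

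The cost is a few sentences and two tables from data already collected, with no change to sample size or conduct. The main downside is imprecision, which the report should show openly. The common-window table needs AE onset dates. It equalises observation time but not the number of sessions: for Tixel it covers all three sessions and about 12 − 4 = 8 weeks after the last.

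### Device-related adverse events are counted over a nominal 16 weeks for Tixel and 12 for LipiFlow, so a crude percentage comparison can be tilted against Tixel, by an amount that depends on event timing

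*Combined protocol and SAP*

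**What the plan says.** Section 4.2.3 sets the endpoint and gives it no time window: "The primary safety endpoint will be a comparison of the incidence of device-related adverse events" in the two arms.

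Section 7.9 supplies the statistic and the window: "The incidence rate of device-related adverse events will be calculated along with 95% CI", and "The reporting period is from baseline through the last study visit". It does not define the term *incidence rate*. Its adverse-event summaries are by patient: "An overall summary will be presented which gives the number and percentage of patients that experienced any TEAE", with a similar count for treatment-related events. No between-arm safety test, common window or person-time denominator is specified.

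Section 6.4 fixes the length of the window in each arm. For Tixel, "each patient will undergo 3 treatment sessions (Day 0, Week 2, Week 4) at 2 weeks intervals (+/-3 days) from the previous treatment", with "follow-up sessions at 4-weeks (+/-7 days) and 12-weeks (+/-14 days) after the last treatment session". LipiFlow patients have one session, on Day 0, and follow-up at the same intervals after it. Section 6.7 confirms that the final visit is counted from the last treatment.

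**The concern.** A reporting period that ends at the last visit looks the same for everyone, but here its length depends on the arm. Tixel's clock for the final visit starts four weeks later, at the third session, while adverse events are collected from the start in both arms. A Tixel patient is therefore watched for longer, and is examined and questioned more often.

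What is at stake is how the primary safety comparison is read. Section 4.2 says the aim is to estimate the size of any differences between the devices, in safety as well as effectiveness. If the Tixel arm shows more patients with an event, the planned output cannot say how much of the excess reflects the device or its three-session course, and how much reflects four more weeks and two more contacts.

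**Working it through.** **The plan's own figure.** No safety quantity is calculated in the plan. The only design calculation, in Section 7.7, is 80% power for a paired t-test on TBUT change with 15 patients. It reproduces: noncentral-t power is 81.1% with 1.5/1.9 = 0.789, and 80.2% with the printed effect size of 0.78. It supplies the 15 per arm used below and has no other bearing on this point.

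**Observation time from Day 0 (Section 6.4).**
- Tixel: 28 + 84 = 112 days. With two intervals of ±3 days and a final window of ±14 days, the range is 92 to 132.
- LipiFlow: 84 days, range 70 to 98.
- Nominal ratio: 112/84 = 1.33.

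Any gap between the baseline examination and Day 0 is ignored, since device-related events cannot arise in it.

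**Contacts at which adverse events are assessed (Sections 6.5 to 6.7).**
- Tixel: Day 0 and weeks 2, 4, 8 and 16, so five.
- LipiFlow: Day 0 and weeks 4 and 12, so three.

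**Case A: equal constant weekly hazard.** The documents give no event rate, so the 12-week incidence p is assumed over a range. The 16-week incidence is 1 − (1 − p)^(112/84).

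| Assumed p, 12 weeks | Same hazard, 16 weeks | Excess, points | Ratio | Extra patients in 15 |
|---|---|---|---|---|
| 5% | 6.6% | 1.6 | 1.32 | 0.24 |
| 10% | 13.1% | 3.1 | 1.31 | 0.47 |
| 20% | 25.7% | 5.7 | 1.29 | 0.86 |
| 30% | 37.8% | 7.8 | 1.26 | 1.18 |
| 50% | 60.3% | 10.3 | 1.21 | 1.55 |

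At p = 10%, moving the Tixel window to its limits of 92 and 132 days gives 10.9% and 15.3%.

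**Against sampling error, p = 10%, 15 per arm.**
- The standard error of the difference is √(0.10 × 0.90/15 + 0.131 × 0.869/15) ≈ 11.7 points, against a shift of 3.1 points.
- Tixel would show more affected patients than LipiFlow with probability 49%, and fewer with probability 29%. Equal windows would give 37.5% each way.
- A two-sided Fisher test, had one been planned, would reject in 1.0% of trials instead of 0.55%.

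**Case B: events follow sessions.** The last four weeks of Tixel observation then add few events, so there is little tilt from time. If each session carried the same risk of, say, 10%, three sessions would give 1 − 0.90³ = 27.1% against 10% for one. That excess belongs to the regimen and should be reported as such.

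**What each denominator does.**
- Patient-weeks are nominally 15 × 16 = 240 for Tixel and 15 × 12 = 180 for LipiFlow. Under Case A the rate ratio is 1. If both arms had the same number k of early events, the ratio would be (k/240)/(k/180) = 0.75, which favours Tixel.
- A 12-week window from first treatment contains all three Tixel sessions, but leaves 12 − 4 = 8 weeks after the last one, against 12 for LipiFlow.
- A 12-week window from last treatment equalises time after treatment, but omits Tixel events before the third session.

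No single summary is neutral under both cases. Together they show which case the data resemble.

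**The case against.** A reader might infer that the comparison is biased against Tixel even when the two devices carry equal risk. The documents do not support that as a general statement. It needs a risk that runs evenly by week and is unrelated to sessions. The endpoint is restricted to device-related events, and Section 6.5 describes erythema, edema and discomfort as effects that follow treatment. Where events follow procedures, more events with three sessions is a true finding. This objection stands, and it limits the size of the tilt. It does not remove the point, because Section 4.2.3 also names lid-margin and lash changes, whose timing the plan does not establish, and the crude percentage cannot separate the two explanations.

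The design also already equalises one reasonable clock: each arm is followed for 12 weeks after its last treatment. That stands too. It is a reason not to make a Day 0 to Day 84 window the sole basis of comparison, which would drop late Tixel events from the primary safety figure. Such a cut has practical problems as well. Day 84 falls between the Tixel visits at weeks 8 and 16, and LipiFlow's final visit may fall as late as day 98.

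The term *incidence rate* could be read as person-time, which would deal with the time component if risk were constant. No such denominator is given, and the other summaries are percentages of patients. Section 7.1 leaves further detail to a statistical analysis plan to be finalised before database lock, so there is room to settle this.

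Finally, the trial is a pilot with 15 per arm and no planned between-arm safety test, and the tilt cannot make Tixel look safer. All of that is true, and it keeps the point modest.

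**Conclusion.** The unequal windows (nominally 112 against 84 days) and contacts (five against three) follow directly from the schedule, and Section 7.9 does nothing to account for them. A comparison of the percentage of patients with a device-related event can therefore be tilted against Tixel.

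The size is uncertain. Under an equal constant weekly hazard and nominal visit timing, the inflation ratio is at most 1.33, and a 12-week incidence of 10%, 20% or 30% becomes about 13%, 26% or 38%. At 10% that is about half a patient in 15, well inside sampling error. Constant hazard is itself an assumption. With events clustered after sessions, the time-related tilt is small and any remaining excess is a real property of the three-session course. The effect of more frequent assessment has the same direction but cannot be quantified from the documents.

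This is an inexpensive improvement to the plan. It is not a fault that invalidates the safety comparison.

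**What to change.** Amend Section 7.9, or the statistical analysis plan before database lock, as follows:

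1. Keep the full-period incidence with its 95% CI as the main figure in each arm, so that no late Tixel event is lost. State that *incidence rate* there means the proportion of patients with at least one device-related event.
2. For the between-arm comparison, add device-related events per patient-week over actual follow-up.
3. Add supportive incidence tables over equal windows, one counted from first treatment and one from last treatment, using onset dates. State how an event first found at a visit is dated.
4. State the unequal number of assessment contacts as a limitation, since none of these summaries corrects for it.

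The cost is a few sentences and one or two more tables. No new visits or data should be needed, because the treatment-emergent definition already depends on onset timing. The patient-week rate assumes roughly even risk over time and can favour Tixel when events come early, so it should be read beside the full-period incidence and not in place of it.
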